1.2 Summary of Nonclinical Studies

A series of non-Good Laboratory Practice (GLP) and GLP nonclinical studies were carried out in order to define the pharmacodynamics (PD), pharmacokinetics (PK), and toxicity of the test product ESN364. Compound affinity to human NK3R and to rat and monkey NK3R orthologs were confirmed via in vitro studies. Receptor-ligand affinity for ESN364 has been confirmed as essentially equipotent for the human and monkey NK3R orthologs. Also, the metabolic stability of the test item was determined to be similar in human and monkey liver microsomes. These preliminary studies justified the use of rat and monkey species in nonclinical testing. Since castrate animals exhibit high and stable levels of plasma LH, castrated rats and monkeys were used as the animal model of choice to measure the PD response to ESN364 in the modulation of plasma LH. Rats and monkeys were used for GLP toxicity studies, and monkeys, as the most sensitive species, were used to define the no observed adverse effect level (NOAEL) and to determine the starting dose in the Phase 1 clinical study.

In the nonclinical toxicology studies in rats and monkeys, ESN364 was well tolerated and the NOAEL was considered to be 25 mg/kg/day in Cynomolgus monkeys, the most relevant species; drug exposure (ie, AUC) at this dose level in Cynomolgus monkey was similar to drug exposure levels measured in premenopausal women dosed at 540 mg/day. The main events that were observed in the nonclinical studies were considered to be related to the pharmacology of ESN364, including reduction of the ovarian activity in female monkeys. Adverse events were only observed at the very high doses used in the nonclinical studies. The NOAEL exceeded the intended clinical doses by a factor of 20. In monkeys, high doses of ESN364 resulted in weight loss and histopathological changes such as hyperplasia of lymphocytes in lymph nodes, spleen, and lung, as well as perivascular inflammation in the kidney. In addition, a reduction in platelet counts considered to be due to decreased production in bone marrow resulted in observations of hemorrhage and regenerative anemia; these effects were recoverable with discontinuation of dosing. In rats, very high dose levels were associated with death and marked clinical signs (including lethargy, reduced activity, labored respiration, and staggering), and body weight loss during the first few days of treatment.

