4.4 Withdrawal Criteria

Subjects have the right to withdraw from the study at any time for any reason, including personal reasons. A subject can withdraw without giving a reason. This will not affect the subject's future care. The Investigator should, however, try to find out why a subject has withdrawn from the study and document the reason for withdrawal in the source documents and on the electronic Case Report Form (eCRF).

A subject **must** be withdrawn from the study or treatment for any of the following reasons:

- Withdrawal of informed consent;
- Lost to follow-up;
- If, for safety reasons, including meeting the requirement for interruption of study drug, it is in the best interest of the subject that she be withdrawn, in the Investigator's opinion;
- Development of a medical condition that requires concomitant treatment with a prohibited therapy (see Section 5.6);
- Development of seizures or other convulsive disorders;
- Breaking of the randomization code during administration of the study drug by the Investigator or by a member of the site staff. If the code is broken by the Sponsor for safety reporting purposes or early timepoint analysis, the subject may remain in the study;
- Confirmed decrease in platelets below 75,000 mm³, which does not normalize after 7 days;
- ALT or AST >8 × ULN;
- ALT or AST >5 × ULN for more than 2 weeks;

- ALT or AST $>3 \times$ ULN **AND** total bilirubin $>2 \times$ ULN or International Normalized Ratio (INR) $>1.5 \times$ ULN; or
- ALT or AST $>3 \times$ ULN with the appearance of fatigue, nausea, vomiting, right upper quadrant pain or tenderness, fever, rash, and/or eosinophilia ($>5\%$).

See Appendix D and Section 9.14 for the procedure to follow in case of suspected drug-induced liver injury (DILI).

In the event that a subject is withdrawn from the study drug, the Medical Monitor and Sponsor or designee should be informed. In the event of withdrawal due to a serious adverse event (SAE), the Sponsor should be notified within 24 hours (for details on adverse event reporting see Section 9.3). In the event of withdrawal for other reasons, the Sponsor or designee should be notified within 2 days of the event.

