9.4 Stopping Rules or Discontinuation Criteria

The study may be stopped for any of the following reasons:

- If ≥ 3 subjects are withdrawn from the study due to a confirmed study-related increase in:
 - ALT or AST $> 8 \times$ ULN;
 - ALT or AST $> 5 \times$ ULN for > 2 weeks;
 - ALT or AST $> 3 \times$ ULN **AND** total bilirubin $> 2 \times$ ULN or INR $> 1.5 \times$ ULN; or
 - ALT or AST $> 3 \times$ ULN with the appearance of fatigue, nausea, vomiting, right upper quadrant pain or tenderness, fever rash, and/or eosinophilia ($> 5\%$);
- If ≥ 3 subjects are withdrawn from the study due to a confirmed study-related decrease in platelets below 75,000 mm³, which does not normalize after 7 days;

- If ≥ 2 subjects develop seizures or other convulsive disorders that are not readily attributable to another underlying disease (eg, brain tumor, head trauma); or
- If an increased frequency of unanticipated deaths or other SAEs is observed.

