7.5.2 Clinical Laboratory Evaluation

The baseline visit is the last measurement taken prior to initial study drug administration.

Quantitative clinical laboratory variables, i.e. hematology, biochemistry, and urinalysis will be summarized using mean, standard deviation, minimum, median, maximum, 10%, 90%, and lower and upper quartiles for each treatment group at each visit. Additionally, a within-subject change will be calculated as the post-baseline measurement minus the baseline measurement and summarized in the same way. Each laboratory result will be classified as low (L), normal (N), or high (H) at each visit according to the laboratory supplied reference ranges.

Shift tables will be generated for each treatment group at each visit.

Frequency tabulations of qualitative clinical laboratory variables (urinalysis) will be presented for each treatment group at each visit (excluding Visits 2A, 3A, and 4A).

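### The SAP has no by-arm count of subjects whose platelets fall below 75,000, the level used in the protocol's withdrawal and stopping criteria

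*SAP*

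**What the plan says.** Protocol 4.4 lists among the mandatory reasons for withdrawal: "Confirmed decrease in platelets below 75,000 mm³, which does not normalize after 7 days". Protocol 9.4 opens with "The study may be stopped for any of the following reasons" and includes the case where three or more "subjects are withdrawn from the study due to a confirmed study-related decrease in platelets below 75,000 mm³", again with the 7-day condition. Protocol 1.2 gives the background: in monkeys at high doses, "a reduction in platelet counts considered to be due to decreased production in bone marrow" was seen, and it was recoverable.

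SAP 7.5.2 summarizes quantitative hematology by arm and visit with mean, SD, minimum, median, maximum, 10th and 90th percentiles and quartiles, and does the same for change from baseline. The categorical rule is: "Each laboratory result will be classified as low (L), normal (N), or high (H) at each visit according to the laboratory supplied reference ranges". The same section also plans shift tables by arm and visit.

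SAP 7.10.6.2 assigns one value to each visit window, the one closest to the target day (the later one in a tie). SAP 7.5 limits safety analyses to data up to one day after the last dose, except adverse events and follow-up visit data.

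SAP 7.5.2.1 treats liver tests differently: it takes each subject's highest value and counts subjects above fixed cut-offs by arm. Platelets have no such table and are not an adverse event of special interest (SAP 7.5.1). The figure 75,000 does not occur in the SAP text supplied.

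**The concern.** Protocol 9.4 has two laboratory-based stopping criteria, liver tests and platelets. The SAP gives the first a worst-value threshold count by arm and the second only the routine hematology summaries. The study compares seven active regimens with placebo, so a reader of the report will want to know how many women in each arm fell to the platelet level the protocol watches for, and whether that number rises with dose. The planned laboratory tables do not answer either question. At stake is how clearly safety is reported, not the efficacy conclusions or the sample size.

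**Working it through.** The plan states no rate or count for this outcome, so there is no figure to reproduce. The inputs are 44 subjects per arm and 8 x 44 = 352 in total (SAP 4), the threshold of 75,000 (Protocol 4.4), the hematology summaries (SAP 7.5.2), the visit windows (SAP 7.10.6.2) and the data cut (SAP 7.5).

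1. **Low class.** The low/normal/high classes use the laboratory's reference range. A count just under the lower limit and a count under 75,000 fall in the same class.

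2. **Minimum.** The by-visit minimum shows whether at least one analysed value was below 75,000. It cannot separate one subject from four.

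3. **10th percentile.** If all 44 subjects have a value, 44 x 0.10 = 4.4, so under the usual SAS definition the 10th percentile is the 5th lowest value. Up to 4 subjects in an arm (4/44 = 9.1%) could be below 75,000 with this percentile still above it.

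4. **Mean.** Assume, for illustration only, that 3 of 44 subjects fall to 70 x 10^9/L from a starting level between 200 and 300. The arm mean moves by 3 x (200 - 70)/44 = 8.9 to 3 x (300 - 70)/44 = 15.7.

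5. **Across visits.** Scheduled on-treatment samples fall at Weeks 2, 4, 6, 8, 10 and 12. By-visit figures cannot be added to give a number of subjects, because one woman may be low at several visits.

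6. **Displacement.** The Week 4 window is Day 23 to Day 36, with target Day 29. A low count on Day 26 is 3 days from target. A retest on Day 30 is 1 day from target, so only the retest enters the Week 4 table. The same can happen in any window where a low count prompts a retest.

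7. **Data cut.** Suppose a low count on Day 43 leads to drug being stopped that day. The cut is Day 44. A retest 7 days later, on Day 50, lies beyond it. The follow-up row takes the last assessment after treatment ends, not the lowest. The end-of-treatment row would probably pick up the Day 43 value, but the retest that decides whether the 4.4 criterion is met need not appear in any by-visit table.

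8. **What a direct count would show.** One subject is 1/44 = 2.3% of an arm. Three subjects are 3/44 = 6.8% (exact 95% CI 1.4% to 18.7%). Three of 44 against 0 of 44 gives a two-sided Fisher p of 0.24, so the table would be descriptive, as safety tables of this size are.

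**The case against.** The strongest reply is that women actually withdrawn for low platelets would be visible elsewhere. Protocol 9.1 asks for clinically significant laboratory findings to be reported as adverse events, and Protocol 9.7 has clinically relevant changes entered in the adverse event section of the eCRF. SAP 7.5.1 then counts, by arm and preferred term, all events, drug-related events and events leading to permanent discontinuation. Three of 44 is 6.8%, above the 5% cut for the common-event table if all three are coded to one term. SAP 7.2.1 adds discontinuation by primary reason. This largely stands for withdrawals. However, these routes depend on the investigator's judgement and on coding, no platelet-specific discontinuation reason is named, and none is tied to 75,000. They may also miss women who fell below 75,000 and recovered.

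The reply that the liver table does not cover every 4.4 liver criterion is also correct: the duration, INR and symptom criteria have no row. The SAP therefore does not follow a rule of one table per withdrawal criterion, and the liver comparison shows a better available method, not a breach. The stopping rule is a pooled count and does not need a by-arm table to operate.

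The nonclinical finding was at high doses and recoverable, and Protocol 1.2 puts the no-adverse-effect level at 20 times the intended clinical doses. The point does not depend on the size of that margin. Finally, Protocol 10 promises subject listings, and the table specifications mentioned in SAP 7.1 are not available here and might already add something.

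A reader might infer three stronger things that the documents do not support:
- **That one count below 75,000 forces withdrawal.** Protocol 4.4 needs a confirmed fall that has not normalized after 7 days, and Protocol 9.4 is permissive and needs three or more study-related withdrawals.
- **That platelets are summarized only by means and shifts.** Minimum, maximum, percentiles and change from baseline are also planned.
- **That three withdrawals would be seen only as low values.** The adverse event and disposition tables make that unlikely.

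**Conclusion.** The gap is real but modest. The laboratory tables in SAP 7.5.2 can show that an analysed platelet value was very low. They cannot give the number of subjects per arm below 75,000 or the number meeting the Protocol 4.4 criterion, and a subject's lowest value can be displaced by a retest or fall after the data cut. In an arm of 44, up to four affected subjects could leave the 10th percentile above the threshold, and three could move the mean by only about 9 to 16 x 10^9/L. The percentile result assumes complete data at the visit and the usual SAS definition; the shift in the mean rests on assumed starting levels that are not in the documents. No power, sample size or efficacy result changes. This is a cheap improvement in safety reporting, not a defect that threatens the trial. No view is taken on whether 75,000 is the right clinical level.

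**What to change.** Add to SAP 7.5.2 one by-arm table based on each subject's lowest platelet count after the first dose. Use all scheduled and unscheduled values through the follow-up visit, and state this window as an exception to the last dose plus one day cut in SAP 7.5 and to the nearest-to-target selection in SAP 7.10.6.2. Show:
- n (%) below the laboratory reference limit;
- n (%) with any value below 75,000;
- separately, n (%) meeting the full Protocol 4.4 criterion (confirmed, and not normalized after 7 days);
- the shift from baseline class to lowest-value class.

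Add a listing of subjects with any value below 75,000 that marks those meeting the full criterion and gives all their platelet values with dates relative to last dose. The denominator should be subjects with at least one platelet value after first dose.

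The cost is one table and one listing from hematology data already collected. No endpoint, visit or clinical rule changes, and the addition can be made before database hard lock and unblinding.

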7.5.2.1 Liver Enzymes and Total Bilirubin

The liver safety assessments will be summarized by the following categories below based on the measurements from Alkaline Phosphatase (ALP), Alanine Transaminase (ALT), total bilirubin, Aspartate Transaminase (AST), and their combinations are defined. These parameters will be measured from a central lab. The subject's highest value during the treatment period will be used.

Parameter	Potentially Clinically Significant Criteria
ALT	>3 x ULN
	>5 x ULN
	>8 x ULN
	>10 x ULN
	>20 x ULN
AST	>3 x ULN
	>5 x ULN
	>8 x ULN
	>10 x ULN
	>20 x ULN
ALT or AST	>3 x ULN
	>5 x ULN
	>8 x ULN
	>10 x ULN
	>20 x ULN
ALP	>1.5 x ULN
Total bilirubin	>1.5 x ULN
	>2 x ULN
ALT or AST and total bilirubin (*)	ALT or AST >3 x ULN and total bilirubin >2 x ULN
ALT or AST, ALP, and total bilirubin (*)	ALT or AST >3 x ULN, ALP <2 x ULN, and total bilirubin >2 x ULN

(*) Combination of values measured within the same day or up to one day apart.

The denominator for each criterion will be the number of subjects who have at least one value during the treatment period. The number and percentage of subjects meeting the criteria during the treatment and follow-up periods will be summarized by treatment group.

A detailed listing will be provided for subjects with suspected drug-induced liver injury (DILI).

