7.5 Analysis of Safety

All analyses of safety will be presented by treatment group for SAF, unless specified otherwise. For analyses by visit, the visit windows from Section 7.10.6 will be applied. Except for adverse events and follow-up visit data, only data up to one day after the last dose date will be considered for the analyses.

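### SAP 7.5.2.1 takes the liver maximum and denominator from the treatment period but counts cases through follow-up, so a higher value two or more days after the last dose can drop out of the by-arm table

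*SAP*

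**What the plan says.** SAP 7.5.2.1 defines the by-arm table of ALT, AST, ALP and total bilirubin thresholds through three statements about period:

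- Value used: the subject's "highest value during the treatment period will be used".
- Denominator: "The denominator for each criterion will be the number of subjects who have at least one value during the treatment period".
- Count: subjects "meeting the criteria during the treatment and follow-up periods will be summarized by treatment group".

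It adds "These parameters will be measured from a central lab", so local results do not enter. The term treatment period is not defined for this table.

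Three other SAP sections bear on the period:

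- 7.5 sets the general rule: "Except for adverse events and follow-up visit data, only data up to one day after the last dose date will be considered".
- 6.2 treats non-adverse-event safety endpoints as treatment-emergent up to one day after the last dose.
- 7.10.6.2 closes the on-treatment safety windows on the day after last exposure.

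On the clinical side, Protocol 9.14.2 monitors for DILI until 21 days after the last dose and withdraws subjects who meet its criteria. Appendix D (section 3.0) asks for repeat liver tests after an elevation, at a frequency that may fall once drug is stopped. Protocol 6.5 includes biochemistry at the ET visit. Protocol 4.4 asks withdrawn subjects back about three weeks after the last intake.

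**The concern.** A worst-value table needs one period for the value, the count and the denominator. Here, if only treatment-period maxima are used, nothing from follow-up can be counted. If follow-up is counted, no rule says which follow-up value is used or who is in the denominator. Reading the count as two separate summaries does not repair this, because the follow-up summary would still have a treatment-period denominator and no value rule.

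The values exposed are those drawn after dosing stops. A subject withdrawn for a liver finding has her later tests off drug, so a rise to a higher ALT/AST threshold or a later bilirubin rise can fall outside the stated maximum. Protocol 5.2 gives selection of a Phase 3 dose as an aim, so by-arm liver rates will be read closely. Two programmers could apply the SAP in good faith and report different counts.

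**Working it through.** The plan gives no figure for this table to reproduce. The check compares the rules and then applies them to assumed series.

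**Step 1. Where an off-drug value lands**

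| Sample | Maximum rule, 7.5.2.1 | Count, 7.5.2.1 | Data cut, 7.5 |
|---|---|---|---|
| Up to last dose + 1 day | in | in | in |
| ET, last dose + 2 or later | out, unless ET is called on-treatment | in, if within follow-up | out, unless called follow-up visit data |
| Unscheduled central test, last dose + 2 or later | out | in, if within follow-up | out, unless called follow-up visit data |
| Follow-up visit | out | in | in (exempt) |

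**Step 2. Status of the ET sample**

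The schedules (Protocol Appendix A, SAP 2.2) place ET with Visit 5 under the treatment period. Protocol 6.5 describes the ET procedures as those of Week 15 (Visit 6). No text requires the ET sample within one day of the last dose.

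**Step 3. Length of the exposed interval**

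DILI monitoring runs to last dose + 21 and the general cut falls at last dose + 1. That leaves 21 - 1 = 20 days of monitoring after the cut, from which only follow-up visit data are exempted.

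**Step 4. Illustrative series (x ULN)**

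The values and the gap to ET are assumed. Last dose is Day 30; on Day 29 ALT is 6 and bilirubin 1.2; the Day 51 return visit is normal.

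| Case | Row | Maximum to last dose + 1 | All values through follow-up |
|---|---|---|---|
| ET Day 34, ALT 12 | ALT >5 | yes (6) | yes (12) |
| | ALT >8 and >10 | no (6) | yes (12) |
| Same, ET on Day 31 | ALT >8 and >10 | yes (12) | yes (12) |
| ET Day 34, ALT 3.5, bilirubin 2.5 | bilirubin >2 | no (1.2) | yes (2.5) |
| | ALT/AST >3 with bilirubin >2 | no | yes |

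The result changes only when the higher value falls at least two days after the last dose.

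**Step 5. Size in one row**

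Inputs: 44 subjects per arm and 7 active arms (SAP 2.1 and Section 4). Assume every subject has an on-treatment value and there is no other case. Intervals are exact two-sided 95%.

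- One arm: 0/44 = 0% (0 to 8.0%; upper limit 1 - 0.025^(1/44)) against 1/44 = 2.3% (0.1 to 12.0%).
- Two such subjects: 2/44 = 4.5%.
- Active arms pooled, 7 x 44 = 308: 0/308 = 0% (0 to 1.2%) against 1/308 = 0.3% (0.01 to 1.8%).

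These show the effect of each omitted subject, not how often omission would occur.

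**The case against.** The case for leaving the text alone has real force.

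- **Most triggering values are on treatment.** An elevation found while dosing continues lies within last dose + 1 day and is counted. In the first series above the subject is in the >3 and >5 rows whichever period is used. Completers are largely unaffected: Protocol 5.5.3 has no on-site dose at Week 12, so that sample normally falls about a day after the last dose.
- **ET may be prompt.** Protocol 4.4 asks for safety assessments of the withdrawal day to be completed. The Protocol 6.5 list also contains Visit 5 items absent from the follow-up list in 6.4 (coagulation, PK, ultrasound), so its Week 15 label may be a slip. This makes a long gap less likely but does not bound the time from last dose to sample.
- **Other outputs exist.** ALT/AST above 3 x ULN is an adverse event of special interest with its own table and listing (SAP 7.5.1), and adverse events are exempt from the one-day cut. Suspected DILI is listed. These are real safeguards, but they give no by-arm laboratory rate for the higher thresholds or for bilirubin.
- **The separate TLF specifications** (SAP 7.1) are not among the documents and may define a window. The SAP text would still conflict with itself.

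Three stronger readings are tempting and are not supported:

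- **That a normal return visit erases an ET peak**, because the follow-up row of 7.10.6.2 keeps the last assessment. SAP 7.5 confines those windows: "For analyses by visit, the visit windows from Section 7.10.6 will be applied". The liver table is not a by-visit analysis.
- **That the combined rows could pair maxima from different weeks.** The table's footnote sets the pairing: "Combination of values measured within the same day or up to one day apart".
- **That rates are materially distorted by cases counted outside the denominator.** This needs a subject with no on-treatment sample, and even then 1/43 = 2.33% compares with 1/44 = 2.27%, about 0.05 percentage points.

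**Conclusion.** The inconsistency is real and lies within SAP 7.5.2.1 itself; 6.2, 7.5 and 7.10.6.2 do not resolve it. Applied as written, the maximum rule can omit a higher ALT, AST or bilirubin value obtained at an ET or unscheduled central-laboratory test two or more days after the last dose. Each omitted subject changes the affected row by 2.3 percentage points in an arm of 44.

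The severity is minor. The conclusion assumes that some withdrawn subjects are sampled more than one day after the last dose and that a new threshold is first crossed then. The documents give no frequency for this, and it is probably low. A reader might infer that DILI cases would go unreported or that the safety conclusions are unsound. The documents do not support that: only this table's counts are at issue, and the special-interest table and the DILI listing remain.

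**What to change.** In SAP 7.5.2.1, use one period for the maximum, the count and the denominator: all scheduled (including ET) and unscheduled central-laboratory values from first dose to the end of follow-up. State this as an explicit exception to the one-day cut in 7.5. If on-treatment rates are also wanted, show them separately, to last dose + 1 day, with their own matching denominator. Leave the one-day pairing footnote as it is.

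The cost is a few sentences and, if the on-treatment view is kept, one more column. Scheduled ET and follow-up samples are already planned, and no clinical threshold or stopping rule changes. The drawback is that some off-drug or unrelated elevations will be counted; a separate on-treatment column would make them visible. The change should be made before unblinding, so that the period is not chosen with the results known.
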